4. STUDY OBJECTIVES

Assess the safety of metformin in diabetic patients undergoing coronary angiography in terms of risk of lactic acidosis. Individuate eventual clinical, echocardiographic predictors of augmented lactic acid after coronary angiography.

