7.2 Secondary endpoints

Contrast-associated acute kidney injury after coronary angiography.

Lactic acidosis development after coronary angiography.

Correlation between clinical, laboratoristic, and echocardiographic variables and lactic acid values.

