8. STUDY POPULATION

8.1. Sample size

In our historical cohort of diabetic patients taking metformin, we observed a mean value of lactic acid of 1.2+0.7 mmol/l.

A total of 106 patients in an estimated time of one years are planned to be enrolled in order to detect with 90% power a prespecified increase of lactic acid of 20% from preprocedural values with a probability of alpha error of

0.05.

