9.2. Pre-enrollment and pre-procedure evaluation (baseline)

Before the inclusion, all patients will undergo to:

- 1. Medical history and physical examination;
- 2. Hemocrome, kidney and liver function, lactic acid evaluation at venous sample;
- 3. CK-MB, hs-troponin I, BNP evaluation at venous sample;
- 4. Transthoracic echocardiography;
- 5. 12-leads electrocardiogram.

9.3. Post-procedure evaluation (the same day after coronary angiography and before hospital discharge)

During postprocedure monitoring (after coronary angiography and before discharge) the following clinical,

laboratoristic, and echocardiographic data will be collected:

- 1. Hemocrome, kidney and liver function, lactic acid evaluation at venous blood sample;
- 2. CK-MB, hs-troponin I, BNP evaluation at venous blood sample;
- 3. Transthoracic echocardiography;
- 4. 12-leads electrocardiogram.
- 5. Lactic acidosis, death, kidney failure, liver failure

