11. STATISTICAL ANALYSES

11.1. Methods

Continuous variables will be reported as mean \pm standard deviation and compared with Student's t test or Mann–Whitney or Wilcoxon tests on the basis of normality of data verified by Kolmogorov–Smirnov goodnessof-fit test. In case of non-normal distribution, variables will be reported as median and interquartile range (IQR). For the primary endpoints of postprocedure lactic acid values, also 95% confidence intervals will be reported. Categorical variables are reported as N (%) and will be compared with χ^2 test without Yates correction for continuity or the Fisher exact test as appropriate. Subgroup analyses will be performed to assess eventual differences in the following subgroups:

- Patients taking other antiglycaemic drugs on top of metformin.
- Patients requiring percutaneous coronary angioplasty.
- Patients with mild and moderate renal function impairment (eGFR<90 and <60 ml/min).

- Patients undergoing urgent coronary angiography (<24 hours from the index event).

Furthermore, linear regression will be performed to assess the correlation between clinical, laboratoristic, and echocardiographic variables with postprocedural lactic acid values.

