11.2. Level of significance

Statistical test will be used to:

- to refuse the null hypothesis of lack of association between metformin continuation and postprocedural increase of lactic acid of 20% from baseline values (primary endpoint) and our secondary endpoints (Ho = metformin continuation not associated with the endpoint)

Association between variables or events will be set at probabilistic level of 5% (p value< 0.05)

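### Any clinical, laboratory or echocardiographic variable can be declared associated with lactate at an unadjusted p<0.05, so the predictor objective can return chance findings

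*Combined protocol and SAP*

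**What the plan says.** Section 4 gives the second of two objectives as: "Individuate eventual clinical, echocardiographic predictors of augmented lactic acid after coronary angiography". Section 7.2 makes the same analysis the last of three secondary endpoints and adds laboratory variables: "Correlation between clinical, laboratoristic, and echocardiographic variables and lactic acid values".

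The method in section 11.1 is a single sentence: "linear regression will be performed to assess the correlation between clinical, laboratoristic, and echocardiographic variables with postprocedural lactic acid values". It does not name the variables, cap their number, choose between one-at-a-time and joint models, or give a selection rule. It also does not say which post-procedural lactate is the outcome. The time schedule in section 1.1 has three draws after baseline: post-procedure, at discharge and at three days.

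Section 11.2 says that testing covers the primary and the secondary endpoints, and then sets the threshold: "Association between variables or events will be set at probabilistic level of 5% (p value< 0.05". Section 11.1 also announces four subgroup items: "Subgroup analyses will be performed to assess eventual differences in the following subgroups". The synopsis calls these prespecified.

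No section of the combined protocol and SAP mentions a multiplicity adjustment, a testing order, validation, or an exploratory status for any of this.

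**The concern.** A 5% threshold limits the false-positive risk of one test. The plan applies it separately to each member of a set that it leaves open, and that set could be large. Section 9.2 collects, besides history, examination and echocardiography, "Hemocrome, kidney and liver function, lactic acid evaluation at venous sample" and "CK-MB, hs-troponin I, BNP evaluation at venous sample". Blood count, renal function and liver function are panels with several results each. Section 9.3 repeats the laboratory tests and the echocardiogram after the procedure, so a candidate could be a baseline or a later value.

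At stake is the credibility of the second objective. A variable that crosses 0.05 by chance could be published as a predictor of raised lactate, and a reader could not tell how many variables were tried to find it.

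**Working it through.** **Inputs**

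- Per-test alpha: 0.05 (section 11.2).
- Number of candidates K: not given. Assumed 10 to 20, with 5 and 30 shown for context.
- Correlation between candidates: not given. Assumed 0, 0.3 and 0.5.
- Patients: 106 (section 8.1). The synopsis says at least 110, which makes no material difference here.

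**The plan's own figure.** Section 8.1 starts from "we observed a mean value of lactic acid of 1.2+0.7 mmol/l", read as mean and SD, and a 20% rise, which is 0.2 × 1.2 = 0.24 mmol/l. The plain paired formula gives n = (0.7 × (1.960 + 1.282) / 0.24)² = 89.4, so 90 (92 with the t distribution). The stated 106 is reached with an allowance that the plan does not state: a signed-rank efficiency of 0.864 gives 106, and so does 15% dropout (90 / 0.85 = 105.9). This does not bear on the present point, where 106 serves only as the number of patients in the simulation.

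**How large is K?** Count each collected item in the classes of section 11.1 once: history, examination, blood count, kidney, liver, CK-MB, troponin, BNP and echocardiography. That is nine. The ECG is collected but is not named in 11.1; with it the count is ten. Because several items are panels, 20 is plausible, but it remains an assumption.

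**Chance of at least one false predictor when none is real.** For independent candidates it is 1 − 0.95^K:

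- K = 5: 1 − 0.95^5 = 0.226
- K = 9: 1 − 0.95^9 = 0.370
- K = 10: 1 − 0.95^10 = 0.401
- K = 20: 1 − 0.95^20 = 0.642
- K = 30: 1 − 0.95^30 = 0.785

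For correlated candidates, simulation with 106 patients, normal null variables and each candidate tested singly (4,000 replicates) gives:

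| K | correlation 0 (formula) | 0.3 | 0.5 |
|---|---|---|---|
| 10 | 40% | 36% | 30% |
| 20 | 64% | 52% | 42% |
| 30 | 79% | 67% | 51% |

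Repeat runs agree within about two percentage points (29% for K = 10 at 0.5; 54% for K = 20 at 0.3).

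**Expected false predictors.** 0.05 × K, whatever the correlation: 0.5 at K = 10 and 1.0 at K = 20.

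**When is a false predictor more likely than not?** For independent candidates, K > ln 0.5 / ln 0.95 = 13.5, so from 14. From the table, about 20 candidates at correlation 0.3 and about 30 at 0.5.

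**What the rule accepts.** With 106 patients, p<0.05 corresponds to a sample correlation above 1.983 / √(104 + 1.983²) = 0.19 in absolute value.

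**What correction would cost.** The correlation detectable with 80% power is tanh((z + 0.842) / √103), where z is the two-sided critical value. Uncorrected, z = 1.960 gives 0.27. With Bonferroni for 20 tests (0.0025 each), z = 3.023 gives 0.36, and the smallest significant sample correlation rises from 0.19 to 0.29.

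**The case against.** The best defence is that this is a secondary analysis in a single-arm study that section 5 describes as observational, and that secondary analyses are often left unadjusted. The threshold sentence can be read as a general alpha statement, and the objective speaks of finding possible predictors, which is close to hypothesis generation. The subgroups are a short, listed set. In a small safety study, correction makes it easier to miss a real predictor.

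Much of this stands. It argues against making a correction mandatory and against treating the matter as a threat to the main result. It does not rescue the text as written. Leaving tests unadjusted is defensible when they are labelled hypothesis-generating, whereas section 11.2 brings the secondary endpoints under formal testing and the label appears nowhere.

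Three stronger readings are tempting, and the documents do not support them.

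- *A false predictor is likely.* That depends on K. At 10 candidates the chance is below one half at every correlation examined, and at 20 it is below one half when the correlation is 0.5.
- *The regression will look explanatory through overfitting.* Section 11.1 does not state a multivariable model, so there is no specified model to criticise on that ground.
- *A false predictor would decide who stops metformin.* No section uses predictors in that way. The only suspension rule, in section 10.2, depends on contrast-induced nephropathy.

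**Conclusion.** The point holds in a limited form. Sections 11.1 and 11.2 together allow any variable in three open classes to be declared associated with post-procedural lactate at an unadjusted 5% level, for a stated objective. Under an assumed 10 to 20 null candidates, the chance of at least one false predictor runs from about 29% (10 candidates, correlation 0.5) to 64% (20, independent), with 0.5 to 1 expected. Even the low end is about six times the nominal 5%.

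These figures assume that no candidate is truly related to lactate, that each is tested once, and that one lactate time point is used. The subgroup comparisons are not included. Neither the primary endpoint nor its sample size is affected. The change should be made, but it concerns what the trial may claim from its secondary analysis.

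**What to change.** **Section 11.1.** Name the candidates, about 10 or fewer, with the time at which each is measured. Percutaneous intervention may be on the list but should be marked as procedural, since the need for it is not generally known before angiography. Name one lactate time point as the outcome and one regression model, and report every coefficient with its 95% confidence interval, whatever its p-value.

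**Section 11.2.** Restrict the p<0.05 rule to the primary endpoint. State that the predictor search and the subgroup comparisons are hypothesis-generating and will be given as estimates with intervals and no significance claim. A short list alone is not enough: five candidates tested at an unadjusted 5% still carry 23% if independent.

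**Only if confirmatory predictor claims are wanted.** Keep the fixed list and apply Holm or false-discovery-rate control. The price is power. As a guide, full Bonferroni over 10 tests (0.005 each, z = 2.807) raises the correlation detectable with 80% power from 0.27 to tanh((2.807 + 0.842) / √103) = 0.34.

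**Cost.** Wording in two sections, with no extra patients or samples. Fewer variables can be called predictors. The other two secondary endpoints, kidney injury and lactic acidosis, would also be reported as estimates with intervals and not as significance tests.

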12. ETHICAL IMPLICATIONS

12.1. General rules

This study will be conducted based on Good Clinical Practices (GCP) and following all Helsinki Declaration principles

12.2. Informed consent

Every enrolled patient will sign and write the data on the approved format of informed consent after explanation of all study related procedures.

13. DATA USE AND PUBLICATION

At the end of data collection and statistical analysis, obtained data will be used for potential publication on internationl scientific journals.

